3.2.2 Secondary Objectives

- Overall survival (OS) in experimental and control arms from date of randomization
- Time to failure of treatment strategy (TFTS) in experimental and control arms after randomization
- PFS rate 1 year after date of randomization
- Depth of response in terms of reduction of tumor mass in experimental and control arms after start of 1st line treatment,
- Metastasis resections in experimental and control arms after start of 1st line treatment
- Objective response rate (ORR) defined as patients with partial or complete response (CR + PR) in experimental and control arms after start of 1st line treatment
- Safety profile according to CTCAE, Version 5.0 criteria in experimental and control arms recorded from the date of signature of Informed Consent

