10.1.2 Secondary Variables

- OS, defined as time from date of randomization until death from any cause; OS should be censored, in patients without an OS event, on the last date they were known to be alive.
- TFTS, is defined as time from date of randomization to failure of treatment strategy defined as treatment discontinuation for any reason, including disease progression, withdrawal of consent, treatment toxicity, patient preference, loss to follow up or death from any cause.
- PFS rate 1 year after date of randomization, derived by Kaplan-Meier method (defined as the estimated rate of patients with progression or death from any cause 1 year after date of randomization)
- Depth of response (DpR) in terms of reduction of tumor mass in experimental and control arms, defined as the percentage of tumor shrinkage, based on longest diameters of all target lesions or reconstructed volume, observed at the lowest point (nadir) compared to baseline. The time for DpR assessment varies between patients relating to the individual achievement of maximal tumor shrinkage, which typically occurs 4–6 months after the start of 1st-line therapy. DpR varies between 100% (= all target tumor lesions have disappeared) and 0% (=no change in tumor size) and has a negative value in cases of increased tumor volume.
- Percentage of patients with metastasis resections, defined as percentage of patients with complete resection of primary tumor and metastases (R0-resection), at any time after the start of 1st line therapy until the end of the treatment strategy.
- ORR, defined as the proportion of randomized patients with CR or PR as best response since start of 1st line therapy.
- Safety, defined as all SAEs regardless of causality, and non-serious adverse events according to CTCAE Version 5.0 criteria, that are definitely, probably, or possibly related to the administration of any study treatment, or that cause permanent discontinuation of treatment, recorded from the date of signature of Informed Consent.

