10.2 Study Populations

The following study populations will be examined:

Modified Intention to Treat (mITT): All randomized patients who received at least 1 dose, complete or incomplete, of study medication

Safety population (SP) = mITT population

Per protocol (PP) population: All randomized patients who received study treatment according to randomization and did not have major disqualifying protocol violations.

Major protocol violations will be stated in the statistical analysis plan (SAP).

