#### Secondary objectives:

- OS in experimental and control arms from date of randomization,
- Time to failure of treatment strategy (TFTS) in experimental and control arms after randomization,
- PFS rate one year after date of randomization,
- Depth of response (DpR) in terms of reduction of tumor mass in experimental and control arms after of first-line treatment,
- Metastatic resections in experimental and control arms after first-line treatment,
- ORR defined as proportion of patients with partial response (PR) or complete response (CR) as best response in experimental and control arms after start of first-line treatment,
- Safety profile according to the National Cancer Institute's (NCI) Common Terminology Criteria of Adverse Events (CTCAE) version 5.0 criteria in experimental and control arms recorded from date of signature of informed consent.

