#### 4.3.9 Safety

Regarding the secondary objective safety, all adverse events (AEs) will be ordered by patient number and summarized in the following listings:

- Terminology and timeline of AE together with causality to study treatments as well as possible actions taken (Listing 28.1) and serious or special classification (Listing 28.2).

Optionally, if the number of AEs is sufficient, then the AEs will be analyzed in frequency tables including number of treatment-related AEs, number of AEs that cause permanent treatment discontinuation, system organ class (SOC) and preferred terms (PT) according to the Medical Dictionary for Regulatory Activities (MedDRA). The following tables will optionally be added:

- An AE overview (Table 4.1), number of AEs with respect to MedDRA grouping and NCI CTCAE grading (Table 4.2), and number of patients with AE by maximal grade with respect to MedDRA coding.

SAEs are classified as special if they involve pregnancy or medication error.

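### By-arm safety is defined from informed consent with no post-randomisation window, so common FOLFIRI toxicity would dilute an arm contrast; the safety variable is also narrower than the adverse events collected and listed

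*Protocol*

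**What the plan says.** - **Window.** Protocol 3.2.2 lists "Safety profile according to CTCAE, Version 5.0 criteria in experimental and control arms recorded from the date of signature of Informed Consent". The synopsis, 10.1 and the definition of the safety variable in 10.1.2 use the same start. SAP 3.4 has "criteria in experimental and control arms recorded from date of signature of informed consent". The time-to-event objectives in the same list (OS, TFTS, one-year PFS rate) run from randomisation.
- **When arms exist.** Under protocol 3.1.2, patients who convert at week 4 or 8 are randomised at week 8, and those who convert at week 12 or 16 at week 16. Until then all receive FOLFIRI or mFOLFIRI every 14 days (5.1).
- **Population.** The safety population equals the mITT set: "All randomized patients who received at least 1 dose, complete or incomplete, of study medication" (10.2). Sections 7.1 and 7.2 call the pre-randomisation FOLFIRI study treatment, so, read literally, the qualifying dose need not follow randomisation.
- **Analysis.** Protocol 10.3 lists the safety summaries without a time window. In SAP 4.3.9, "all adverse events (AEs) will be ordered by patient number and summarized in the following listings", with optional frequency tables.
- **What counts.** Protocol 10.1.2 has "Safety, defined as all SAEs regardless of causality", and limits the rest to those "that are definitely, probably, or possibly related to the administration of any study treatment, or that cause permanent discontinuation of treatment". The opening of Section 9 requires AEs to be reported up to 30 days after the last dose, and 9.5 captures all AEs with their relationship to treatment. Neither sets a causality limit in that period.
- **AE start date.** The opening of Section 9 and, for SAEs, 9.5 start at consent. Footnote 13 to the schedule of assessments starts at the first administration of study treatment.

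**The concern.** An event before allocation cannot be an effect of the arm. Every randomised patient brings 8 or 16 weeks of the same chemotherapy, about four or eight cycles, into a comparison that is meant to show what intermittent cetuximab adds. If those weeks count, both arms gain the same background and the contrast moves towards no difference. This affects toxicities that FOLFIRI also causes.

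The second issue is which events the endpoint includes. The trial is open-label, so causality is judged by an investigator who knows the arm. A variable that keeps a non-serious AE only if it is judged related, or if it ends treatment, depends partly on that judgement. The rest of the protocol and the SAP use a wider set.

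**Working it through.** **1. Figures in the plan.** The documents give no figure for the safety comparison and no FOLFIRI adverse event rates. The planning values used below are 58 patients per arm and a 12-month control PFS of 30% (protocol 10.4). They are coherent with the rest of that section: ln(0.5)/ln(0.3) = 0.5757, as stated. Freedman's formula gives 108.3 events unrounded against the stated 107. Exponential PFS with 18 months of accrual and 0.25% monthly drop-out gives 107.0 expected events at 52 months. The safety point does not depend on this sample size calculation.

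**2. Dilution of a shared toxicity.** Let q be the risk of at least one event before randomisation, the same in both arms, and p the risk after it. If the two are independent within a patient, the risk counted from consent is q + (1 − q)p. The difference is therefore (1 − q)(pA − pB). Assumed: pB = 30%, pA = 50%, with q varied.

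| q | Arm B from consent | Arm A from consent | Difference (points) | Risk ratio |
|---|---|---|---|---|
| 0 (counted from randomisation) | 30% | 50% | 20 | 1.67 |
| 0.1 | 37% | 55% | 18 | 1.49 |
| 0.2 | 44% | 60% | 16 | 1.36 |
| 0.3 | 51% | 65% | 14 | 1.27 |
| 0.5 | 65% | 75% | 10 | 1.15 |

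For q = 0.3: 1 − 0.7 × 0.7 = 0.51 and 1 − 0.7 × 0.5 = 0.65. If such a difference were tested at two-sided 5% with 58 per arm (no such test is planned), power would fall from 60% to 33%. Without independence, the difference from consent is (1 − q) times the difference among patients with no earlier event, so the factor is then only approximate.

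**3. A cetuximab-specific toxicity.** Protocol 2.3.3 gives grade 3 or 4 skin reactions in 15.7%. Assume 0 to 1% in Arm B and q of 0 to 2%. With q = 2%, the difference goes from 15.7 to 0.98 × 15.7 = 15.4 points, or from 14.7 to 0.98 × 14.7 = 14.4 points. The loss is at most 0.3 points. This concerns the difference; a ratio against a near-zero control rate moves more.

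**4. Share of treatment time.** The control hazard is −ln(0.3)/12 per month, so median PFS is 6.9 months. With 30.4 days per month (SAP 4.12), 8 weeks are 1.84 months and 16 weeks 3.68 months. If treatment runs to progression, the common phase is 1.84/(1.84 + 6.91) = 21% or 3.68/(3.68 + 6.91) = 35% of that total. An assumed true rate ratio of 1.5 after randomisation, with equal treatment time in both arms, would appear as (1.84 + 1.5 × 6.91)/(1.84 + 6.91) = 1.39, or as 1.33 with 16 weeks.

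**5. What the current SAP prints.** Table 4.1 has columns for the four drugs and a total. Tables 4.2 and 4.3 are pooled by grade. All three are optional. Listings 28.1 and 28.2 show the arm and the AE start date but not the trial phase. Listing 28.1 has a flag for study treatment having started, which does not separate the phases because study treatment starts before randomisation. Listing 3 gives the randomisation date.

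**6. Which non-serious AEs count.**

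| Non-serious AE | Variable in protocol 10.1.2 | Collection, protocol Section 9 and 9.5 | SAP 4.3.9 listings |
|---|---|---|---|
| Judged related | in | in | in |
| Judged unrelated, causes permanent discontinuation | in | in | in |
| Judged unrelated, no permanent discontinuation | **out** | in | in |

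**The case against.** The consent start can be read as a collection rule, and collecting from consent is sound. No planned table gives an AE rate by arm. SAP 4.2 reports that enrolment closed at seven patients and turns most analyses into listings. Point and interval estimates (4.7) and significance levels (4.19) are not applicable. For seven patients, anyone can place an event before or after randomisation by reading two dates. All of this stands for the current report. It does not supply a window: 10.1.2 makes the consent start part of the variable's definition, the objective names the arms, and nothing in 10.3 or SAP 4.3.9 narrows it.

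Four stronger readings are tempting, and the documents do not support them.

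- *Cetuximab's added toxicity is masked.* Cetuximab is not given before randomisation, and its specific reactions are hardly diluted (step 3). Listing 28.1 also records causality by drug component.
- *The trial will report understated toxicity through Tables 4.1 and 4.3.* Neither table has arm columns, and no between-arm estimate is planned.
- *Unrelated non-serious AEs are lost.* They fall outside one variable definition, but they are still captured and listed. Table 4.1 already has separate rows for any AE and for treatment-related AEs.
- *The AE listings alone lack a time point.* Listings 17.2, 20.2 and 23.2 also identify the visit only by date or staging number.

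**Conclusion.** The point holds as a defect of definition. The protocol compares safety between arms from a date 8 to 16 weeks or more before arms exist, and sets no post-randomisation window. A by-arm summary made to that rule would multiply the risk difference for toxicities shared with FOLFIRI by about 1 − q. With assumed q from 0.1 to 0.5, 20 points become 18 to 10. This rests on assumed rates and on independence within patients; the direction follows from the common phase. Differences in cetuximab-specific reactions barely change.

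For the seven-patient report the consequence is small: the arm is printed beside pre-randomisation events without a phase label. The safety variable is a conflict between definitions, with no loss of data. The AE start date is a further contradiction that must be reconciled.

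**What to change.** - In protocol 10.1.2 and 10.3 and SAP 4.3.9, base any by-arm safety summary on AEs that start or worsen on or after the first dose following randomisation. Report AEs from consent to randomisation separately and pooled. State where an AE between randomisation and that first dose belongs, and how a patient with no dose after randomisation is handled.
- Add a pre-/post-randomisation flag to Listings 28.1 and 28.2, from the AE start date and the randomisation date.
- Define the safety variable as all AEs regardless of causality, with related AEs as a subset.
- Reconcile the AE start date between footnote 13 and protocol 3.2.2, the opening of Section 9, and 10.1.2.

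The cost is wording and one derived flag from dates already collected. Worsening can be derived only if a change of grade is entered as a new record, which the documents do not say, so the SAP should state the convention.

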3.2.3 Exploratory objectives (optional)

- To identify driver mutations (e.g. BRAF, PI3K-AKT-mTOR etc.) in patients with progressive disease (PD) under cetuximab therapy who remain *RAS* wild-type in liquid biopsy
- To compare the efficacy in terms of progression free survival (PFS) in patients with conversion to *RAS* wild-type in ddPCR and BEAMing with those patients showing conversion to *RAS* wild-type in ddPCR but not in BEAMing

3.3 Study Population and Justification of Choice of Gender

The selection of patients occurs through the investigator according to the inclusion and exclusion criteria after informing the patient written and orally about the study and after the patient has signed the informed consent. No gender specific differences are expected concerning the efficacy and safety of the study treatment, hence there is no preferred enrolment of men or women within this study. However, pregnant or breast-feeding women are excluded from participation.

3.3.1 Inclusion Criteria

Patients may be **included** in the study only if they meet **all** the following criteria:

- Histologically confirmed, UICC stage IV adenocarcinoma of the left-sided colon or rectum with metastases (metastatic colorectal cancer), primarily non-resectable, confirmed RAS mutations proven in the primary tumor or metastasis (KRAS and NRAS exon 2, 3, 4)
- Age ≥ 18 years on day of signing informed consent
- No previous chemotherapy for metastatic disease (1 - 2 cycles FOLFIRI or mFOLFIRI are permitted before enrolment until RAS status is determined)

- Patients suitable for chemotherapy administration
- ECOG performance status 0-1
- Consent to liquid biopsy and mutation analysis
- Estimated life expectancy > 3 months
- Presence of at least one measurable reference lesion according to the RECIST 1.1 criteria (chest CT and abdominal CT 4 weeks or less before enrollment)
- Adequate bone marrow function defined as:
 - Leukocytes $3.0 \times 10^9/L$ with neutrophils $1.5 \times 10^9/L$
 - Thrombocytes $100 \times 10^9/L$
 - Hemoglobin 9 g/dL
- Adequate hepatic function defined as:
 - Serum bilirubin $1.5 \times ULN$
 - ALAT and ASAT $2.5 \times ULN$ (in the presence of hepatic metastases, ALAT and ASAT $5 \times ULN$)
- Adequate renal function: Creatinine clearance $\geq 50 \text{ mL/min}$
- Adequate cardiac function defined as
 - Normal ECG and echocardiogram with a left ventricular ejection fraction (LVEF) of 55%
- INR < 1.5 and aPTT < 1.5 $\times ULN$ (patients without anticoagulation). Therapeutic anticoagulation is allowed if INR and aPTT have remained stable within the therapeutic range for at least 2 weeks.
- Time interval of at least 6 months since last administration of any previous neoadjuvant/adjuvant chemotherapy or radiochemotherapy of the primary tumor in curative treatment intention
- Any relevant toxicities of prior treatments must have resolved to grade ≤ 1 according to the CTCAE (version 5), except alopecia
- Women of childbearing potential (WOCBP) should have a negative urine pregnancy test within 72 hours prior to receiving the first dose of study medication.
- Highly effective contraception for both male and female patients throughout the study and for at least 3 months after last dose of study medication administration if the risk of conception exists. Highly effective contraception has to be in line with the definition of the CTFG recommendation (see 17.5)
- Signed written informed consent and capacity to understand the informed consent

3.3.2 Exclusion Criteria

Patients will be **excluded** from the study for **any** of the following reasons:

- Right sided mCRC
- Primarily resectable metastases
- Previous chemotherapy for the colorectal cancer with the exception of adjuvant treatment, completed at least 6 months before entering the study (1-2 cycles of FOLFIRI or mFOLFIRI are permitted before enrolment)
- Patients with known brain metastases
- Symptomatic peritoneal carcinosis
- Progressive disease before randomization
- History of acute or subacute intestinal occlusion, inflammatory bowel disease, immune colitis or chronic diarrhea

- Grade II heart failure (NYHA classification), Myocardial infarction, balloon angioplasty (PTCA) with or without stenting, and cerebral vascular accident/stroke within the past 12 months before enrollment, unstable angina pectoris, serious cardiac arrhythmia according to investigator's judgment requiring medication
- Medical or psychological impairments associated with restricted ability to give consent or not allowing conduct of the study
- Active infection with hepatitis B or C
- Additional cancer; Exceptions include adequately treated basal cell carcinoma of the skin, squamous cell carcinoma of the skin, or in situ cervical cancer that has undergone potentially curative therapy without evidence of recurrence
- Uncontrolled hypertension
- Marked proteinuria (nephrotic syndrome)
- Arterial thromboembolism or severe hemorrhage within 6 months prior to randomization (with the exception of tumor bleeding before tumor resection surgery)
- Hemorrhagic diathesis or tendency towards thrombosis
- Participation in a clinical study or experimental drug treatment within 30 days prior to study
- Known hypersensitivity or allergic reaction to any of the study medications
- Severe, non-healing wounds, ulcers, bone fractures or an infection requiring systemic therapy
- Known history of alcohol or drug abuse
- Complete dihydropyrimidine dehydrogenase (DPD) deficiency (phenotyp and/or genotype test)

(Patients with partial DPD deficiency may be included and should receive the first cycle with a reduced 5-FU dose. Dose reduction and escalation are at the discretion of the investigator and must be determined in the best interest of the patient.)
- Known glucuronidation deficiency (Gilbert's syndrome) (specific screening not required)
- Absent or restricted legal capacity
- For female patients only: Pregnancy (absence to be confirmed by β -HCG test) or lactating

3.3.3 Enrolment of Patients

Only patients who meet the inclusion and exclusion criteria are selected and enrolled by online registration.

Online registration is possible 24 hours a day. After the registration form has been saved, a registration number is notified immediately by an automatically generated fax to the investigator.

Patients who are not registered, but sign informed consent and undergo at least some of the selection procedures will be considered screening failures. A record of these patients will be maintained by the study site.

After registration, treatment with FOLFIRI/mFOLFIRI should be instituted within a maximum interval of 14 days.

Patients who are registered but who are not treated within 14 days can be treated under the same patient number after further examinations to make sure that all inclusion and exclusion criteria are still met.

4 Study Treatment

All medications used as study treatment will be prescribed according to routine clinical practice. The drugs will be stored, prepared and administered according to the respective SmPC. Except for cetuximab (Erbilux®, Merck), all other drugs are specified by active substance only within this study.

5 Treatment Plan

5.1 *Treatment Regimen*

The 1st-line therapy is defined as all treatment from start of FOLFIRI / mFOLFIRI (date of the 1st cycle either in the pre-screening or the pre-randomization phase) until progressive disease (PD), unacceptable toxicity, withdrawal of informed consent, loss to follow-up, patient preference, or death.

One cycle consists of 14 days. Drugs will be administered according to each center's routine.

Pre-randomization phase:

Patients will be treated with FOLFIRI. The 5-FU bolus may be omitted at the investigator's discretion to achieve better therapy tolerability (mFOLFIRI).

FOLFIRI (q14d):

- Irinotecan 180 mg/m² iv, 30 - 90 min on day 1
- Folinic acid (racemic) 400 mg/m² iv, 120 min on day 1
- 5-FU 400 mg/m² bolus on day 1
- 5-FU 2400 mg/m² iv over 46 h on day 1-2

OR

mFOLFIRI (q14d):

- Irinotecan 180 mg/m² iv, 30 - 90 min on day 1
- Folinic acid (racemic) 400 mg/m² iv, 120 min on day 1
- 5-FU 2400 mg/m² iv over 46 h on day 1-2

Patients with partial DPD deficiency should receive the first cycle of FOLFIRI with a reduced 5-FU dose. Dose reduction and escalation are at the discretion of the investigator and must be determined in the best interest of the patient.

One or two cycles of FOLFIRI/mFOLFIRI may be administered in the pre-screening period before the result of the RAS analysis is available. Patients with any RAS mutation who fulfill all the eligibility criteria will be enrolled into the pre-randomization phase. Patients with RAS wild-type status will be considered screening-failures.

Randomized phase

Control arm:

FOLFIRI (q14d):

- Irinotecan 180 mg/m² iv, 30 - 90 min on day 1
- Folinic acid (racemic) 400 mg/m² iv, 120 min on day 1

- 5-FU 400 mg/m² bolus on day 1
- 5-FU 2400 mg/m² iv over 46 h on day 1-2

OR

mFOLFIRI (q14d):

- Irinotecan 180 mg/m² iv, 30 - 90 min on day 1
- Folinic acid (racemic) 400 mg/m² iv, 120 min on day 1
- 5-FU 2400 mg/m² iv over 46 h on day 1-2

Experimental arm (switch arm):

FOLFIRI (q14d) + cetuximab (q1w):

- Irinotecan 180 mg/m² iv, 30 - 90 min on day 1
- Folinic acid (racemic) 400 mg/m² iv, 120 min on day 1
- 5-FU 400 mg/m² bolus on day 1
- 5-FU 2400 mg/m² iv over 46 h on day 1-2
- Cetuximab initially 400 mg/m² as a 120 min infusion (\leq 5 mg/min) on day 1; subsequently 250 mg/m² iv as a 60 min infusion every week (\leq 10 mg/min)

OR

mFOLFIRI (q14d) + cetuximab (q1w):

- Irinotecan 180 mg/m² iv, 30 - 90 min on day 1
- Folinic acid (racemic) 400 mg/m² iv, 120 min on day 1
- 5-FU 2400 mg/m² iv over 46 h on day 1-2
- Cetuximab initially 400 mg/m² as a 120 min infusion (\leq 5 mg/min) on day 1; subsequently 250 mg/m² iv as a 60 min infusion every week (\leq 10 mg/min)

If *RAS* wild-type converts to *RAS* mutant:

FOLFIRI or mFOLFIRI (q14d) as stated above

If *RAS* mutant converts to *RAS* wild-type again:

FOLFIRI or mFOLFIRI (q14d) + cetuximab q1w as stated above

In case one of the substances has to be stopped due to toxicity, the others should be continued, if tolerable for the patient.

